### Analysis methods

	Metric to be reported	Method of calculation
Primary outcome		
1. TB treatment initiation	Risk ratio of TB treatment initiation by allocation arm.  We will also calculate and report absolute risk difference.	Regression using robust standard errors to account for clustering. GLM with log-link and binomial distribution to approximate risk ratio.*  Absolute risk difference will be obtained from binomial GLM with identity link function.

Secondary outcomes		
2. Mortality	Hazard ratio for death (time to event)	Cox regression using robust standard errors to account for clustering.
3. Same day TB treatment initiation	Risk ratio of TB treatment initiation within 24 hours from enrolment by allocation arm.	Regression using robust standard errors to account for clustering. GLM with log-link and binomial distribution to approximate risk ratio.*
4. Undiagnosed TB	Risk ratio of undiagnosed TB by allocation arm.	Regression using robust standard errors to account for clustering. GLM with log-link and binomial distribution to approximate risk ratio.*

Other outcomes		
5. Inpatient mortality	Risk of death prior to discharge from hospital.	Regression using robust standard errors to account for clustering. GLM with log-link and binomial distribution to approximate risk ratio.*
6. 56 day mortality (measured as a proportion)	Risk of death within 56 days from enrolment (i.e. analysed as a proportion rather than time to event)	Regression using robust standard errors to account for clustering. GLM with log-link and binomial distribution to approximate risk ratio.*
7. Microbiologically confirmed TB.	Proportion of TB	Numerator is those with microbiologically confirmed TB and denominator is all who had TB diagnosed.
8. Intervention fidelity	Proportion	Numerator is all those who received DCXR with valid CAD score and a FujiLAM urine result, denominator is all those recruited in clusters allocated to intervention arm.

## Notes on analysis methods

\* If GLM with log-binomial link function fails to converge then we will use an alternative method to calculate risk ratio, or report an odds ratio. *Sensitivity analyses*

If there are large numbers (>5%) of participants who do not receive their allocated intervention, then we will perform a sensitivity analysis on a per-protocol basis, where outcomes are based on intervention actually received rather than intervention each cluster was allocated to.

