### Sample size

We plan to recruit 102 clusters per trial arm.

Sample size was calculated for primary outcome (TB treatment initiation). We assumed 10% people in usual care arm would initiate TB treatment by the time of hospital discharge, and 18% of people in intervention arm would initiate TB treatment. We assumed clusters with three participants per cluster and minimal clustering of outcome (ICC of 0.005).

[figure not shown]
Sample size for primary outcome was calculated in R using 'clusterPower' package

```
library(clusterPower)
p_int <- c(0.12,0.14,0.16,0.18,0.20,0.22)
pwr_3 <- crtpwr.2prop(alpha = 0.05, power = NA, m = 102, n = 3, cv = 0.1, p1 = p_int, p2 = 0.1, icc =
0.005, pooled = FALSE, p1inc = TRUE)
```

Sample size for secondary outcome was calculated in stata using below command (assuming 80% survival by 56 days):

```
power logrank 0.8, k1(102) m1(3,4) hratio(0.6,0.65,0.7,0.75,0.8) rho(0.005) cvcluster(0.05)
```

If there were three participants per cluster, K 0.005 and TB treatment initiations 10% in usual care and 18% in intervention arm, then with 102 clusters per arm we will have 81% power to detect a difference between arms at least that large.

For secondary (survival) outcome, if there are four people per cluster and a hazard ratio of 0.6 (ICC 0.005 and survival probability 80% in usual care group) then with 102 clusters per arm we could have 81.6% power to detect an effect at least that large. With three people per cluster the power drops to 69.9%.

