### **Adherence and protocol deviations**

Adherence to intervention is defined as receiving a DCXR and urine LAM test (for those in intervention arm). Analysis is intention-to-treat and is not affected by adherence to intervention.

Protocol deviations are defined in LSHTM-SOP-012-02 (LSHTM Research Governance and Integrity Office, 2019-11-28). Major and minor protocol deviations and any protocol violations will be summarised in an appendix to main trial paper.

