### **Analysis populations**

CASTLE will be analysed on an intention to treat basis.

The analysis population will include all randomised participants according to the intervention their cluster was randomised to receive, regardless of whether the intervention was received or not.

Participants enrolled into a randomised cluster who were subsequently found to be ineligible for the CASTLE trial will be removed from analysis.

Should there be a major protocol deviation / violation involving large numbers of participants not receiving the intervention to which their cluster was assigned, we would consider a per protocol additional analysis.

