### Baseline participant characteristics

Baseline participant characteristics for categorical variables will be summarised by frequencies and percentages. Continuous data (age, CD4 count) will be summarised by median and interquartile range. Tests of statistical significance will not be undertaken for baseline characteristics; rather the clinical importance of any imbalance will be noted.

The primary analysis will be unadjusted for baseline characteristics. If there is a major imbalance in baseline characteristics, we would consider a secondary sensitivity analysis adjusted for the imbalanced variable.

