4. Proportion with undiagnosed TB.	Sputum culture at mycobacterial lab in Blantyre grows M. tuberculosis complex organisms and participant did not start TB treatment at or before time of discharge from hospital or death or 56 days from enrolment (whichever is sooner).	TB treatment initiation as defined in primary outcome.	People whose sputum grows non-tuberculous mycobacteria are not included as having undiagnosed TB. People who start TB treatment but who subsequently interrupt TB treat are not treated as having undiagnosed TB. Denominator is all people in CASTLE trial, not just those who produce sputum.
Other outcomes / measurements			
Inpatient mortality	Death from any cause	From time of enrolment until time of hospital discharge or 56	Determined through observation, notes review, asking healthcare staff and the ward paper ledger.

		days from enrolment, whichever is sooner.	
56 day mortality (measured as a proportion)	Death from any cause	From time of enrolment in CASTLE trial to 56 days from enrolment. Analysed as binary data.	In hospital deaths determined as above, deaths after discharge from hospital ascertained from phone-call with nominated next of kin.
Microbiologically confirmed TB.	Proportion of all TB diagnoses that are microbiologically confirmed.	Refers to TB diagnoses made before discharge from hospital or before 56 days from enrolment, whichever is sooner.	Microbiologically confirmed means at least two positive Acid Fast Bacilli (AFB) smears or one or more Xpert Mtb/Rif positive or one or more culture positive for M. tb on any specimen or a positive urine LAM result. Includes samples collected by CASTLE team and those by usual care team.
Intervention fidelity	Proportion of people recruited in intervention clusters who have a CxR with CAD score and urine LAM result recorded	We will record any instance where intervention not delivered on the same day as enrolment.	Reasons for not receiving interventions will also be detailed.

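### The conditional sensitivity analysis called per-protocol groups participants by intervention received, so it is an as-treated comparison whose mortality result can be biased; ITT is unaffected

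*SAP*

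**What the plan says.** The main analysis is by allocation. SAP section 4, Adherence and protocol deviations, states: "Analysis is intention-to-treat and is not affected by adherence to intervention". Analysis populations, in the same section, likewise assigns participants to the arm their cluster was randomised to, whether or not the intervention was delivered.

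Two places provide for a further analysis when delivery fails:

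- **Section 4, Analysis populations.** After a major deviation affecting many participants, "we would consider a per protocol additional analysis". No numerical threshold is given.
- **Section 6, Notes on analysis methods (Sensitivity analyses).** Above 5% non-receipt the analysis is a firm commitment. It is done on a "per-protocol basis, where outcomes are based on intervention actually received rather than intervention each cluster was allocated to". The sentence is not limited to the primary outcome, so mortality is included.

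Receipt is worded in three ways:

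- **Section 4, Adherence:** "Adherence to intervention is defined as receiving a DCXR and urine LAM test (for those in intervention arm").
- **Section 6, Outcome definitions, intervention fidelity:** participants who "have a CxR with CAD score and urine LAM result recorded".
- **Section 6, Analysis methods, item 8:** a valid CAD score plus a FujiLAM result, among those recruited in intervention clusters.

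Section 3, Trial design, gives the intervention arm FujiLAM, AlereLAM and DCXR-CAD, and also allows AlereLAM in usual care on clinician request.

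**The concern.** A per-protocol analysis normally keeps the allocated arms and restricts to those who adhered. The SAP's definition lets receipt decide the group. An intervention-arm patient who was never tested would then, on the natural reading, be counted with usual care.

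The SAP itself shows how receipt could depend on prognosis. Outcome definitions provides for deaths on the day of enrolment (credited with half a day of survival). The fidelity entry provides for delivery that does not happen on that day. A patient who dies before testing would leave the intervention group and add a death to the comparison group, although follow-up starts at enrolment for everyone.

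The passage specifies no adjustment for this selection. Elsewhere, Missing data says that no baseline adjustment is planned. Baseline participant characteristics says only that, for a major imbalance, "we would consider a secondary sensitivity analysis adjusted for the imbalanced variable", and does not link this to analysis by receipt. The fidelity entry promises "Reasons for not receiving interventions will also be detailed". That helps a reader judge the selection but does not remove it.

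The passage also does not say how a patient with DCXR but no LAM result, or the reverse, is classed. So who changes group is not fixed in advance.

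**Working it through.** **The plan's own figures.** Sample size plans mortality "assuming 80% survival by 56 days", that is 20% deaths in usual care. Its survival power can be reproduced with the Freedman log-rank formula and a design effect. With 3 per cluster and hazard ratio 0.6:

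- Expected events = 306 × 0.20 + 306 × (1 − 0.8^0.6) = 61.2 + 38.3 = 99.5.
- Design effect = 1 + ((1 + 0.05²) × 3 − 1) × 0.005 = 1.010.
- Power = Φ(√(99.5/1.010) × 0.4/1.6 − 1.96) = 69.9%, as stated.

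With 4 per cluster (132.7 events) it is 81.6%, also as stated. No printed number is in error; the issue is the grouping rule.

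**Bias under no true effect.** Inputs:

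- p = 0.20, 56-day mortality in both arms (SAP planning figure).
- f = share of the intervention arm counted with usual care (assumed; not in the SAP).
- k = mortality of the untested relative to the tested (assumed; not in the SAP).

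Formulas, with equal arm sizes:

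- Risk in the tested: r = p / (1 − f + f·k).
- Risk in the untested: m = k·r.
- Risk in the as-treated usual-care group: u = (p + f·m) / (1 + f).
- As-treated risk ratio = r / u. The intention-to-treat risk ratio is 1.00.

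Worked cell, f = 0.06 and k = 1.5: r = 0.20/1.03 = 0.1942; m = 0.2913; u = (0.20 + 0.0175)/1.06 = 0.2052; ratio = 0.946.

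| f | k | r | u | As-treated RR | RR if the untested are excluded (r/p) |
|---|---|---|---|---|---|
| 6% | 1 | 0.2000 | 0.2000 | 1.00 | 1.00 |
| 6% | 1.5 | 0.1942 | 0.2052 | 0.95 | 0.97 |
| 6% | 2 | 0.1887 | 0.2100 | 0.90 | 0.94 |
| 10% | 1 | 0.2000 | 0.2000 | 1.00 | 1.00 |
| 10% | 1.5 | 0.1905 | 0.2078 | 0.92 | 0.95 |
| 10% | 2 | 0.1818 | 0.2149 | 0.85 | 0.91 |

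The last column shows that a conventional per-protocol restriction reduces the bias but does not remove it.

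**Effect of the unclassified partly tested.** If 6% lack full receipt but half of them stay in the intervention group, f falls to 3%. The ratio is then 0.97 (k = 1.5) or 0.94 (k = 2), against 0.95 and 0.90 when all 6% are moved.

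**Chance of a spurious result.** In simulation (102 clusters of 3 per arm, ICC 0.005, cluster-robust test, nominal two-sided 5%), the as-treated test rejects about 6% and 9% of the time at f = 6% for k = 1.5 and 2. At f = 10% it rejects about 9% and 16%. Intention-to-treat stays at about 5%.

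**TB treatment initiation.** Take 18% in the tested, 10% in usual care and f = 10%. If the untested start treatment at 5%, the as-treated ratio is 0.18/((0.10 + 0.005)/1.1) = 1.89 against 1.67 by intention-to-treat. If they start at 15%, it is 0.18/((0.10 + 0.015)/1.1) = 1.72 against 1.77. The shift can go either way, so no direction is claimed.

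**The case against.** The strongest reply is that little depends on this. The analysis is secondary to intention-to-treat and runs only above 5% non-receipt. Nothing in the SAP suggests that the trigger will be met, and the sentence openly states its grouping rule. All of this stands and is why the point is minor. It does not correct the label: a reader told that an analysis is per-protocol would not expect untested intervention patients to be counted with usual care.

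The size is assumed. Neither f nor k is in the SAP. This also stands, and it limits what may be inferred. Four stronger readings are tempting:

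- **That the bias is large.** With k = 3 the ratio falls to 0.82 at 6% and 0.73 at 10%. But that implies mortality of 54% in the untested against 18% in the tested, or 50% against 17%. The SAP gives no basis for such figures.
- **That the Cox hazard ratio is biased by these amounts.** The figures are for the 56-day proportion, which the SAP lists among other outcomes. The secondary mortality outcome is a hazard ratio, for which no bias was computed.
- **That the SAP rules out adjustment here.** The Missing data statement explains why missing covariates do not matter, and the baseline section concerns imbalance between arms. On adjustment in this analysis the SAP is silent.
- **That the SAP says outright that untested patients join usual care.** It does not; the wording implies it.

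**Conclusion.** The point holds as a minor one. The label and the definition conflict within one sentence. Followed as written, the rule produces a comparison without the protection of randomisation and with no adjustment specified.

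The harm is conditional on three things: non-receipt above 5%, worse prognosis in the untested, and the untested being counted with usual care. Under those conditions mortality is shifted in favour of the intervention, by about 5% to 10% on the risk-ratio scale at 6% non-receipt and 8% to 15% at 10%, for 1.5 to 2 times the risk. With equal prognosis there is no bias.

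A reader might infer that the trial's main conclusions are at risk. The documents do not support that, because all main results are by allocation.

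**What to change.** 1. Remove the regrouping by receipt from Notes on analysis methods. Above the 5% trigger, use a sensitivity analysis that keeps everyone in the allocated arm. One option is a complier-average risk difference with cluster allocation as the instrument and cluster-based confidence intervals. For mortality it would supplement the Cox hazard ratio, not replace it.
2. For that estimate, count as non-receivers only those who received no intervention component. The method assumes that allocation has no effect in non-receivers. That is doubtful for a patient who had DCXR but no LAM result, and plausible for one who had nothing. State the assumption.
3. If an analysis by receipt is still shown, label it 'as-treated, exploratory'. Say how partly tested patients are classed, and state that its mortality result is open to bias from early death and illness severity.
4. Reconcile the three wordings of receipt with Trial design, including whether AlereLAM counts, since both arms can have it. State whether the base for the 5% is the intervention arm or all participants. Align the conditional wording in Analysis populations with the firm commitment in section 6.

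**Cost.** This needs SAP wording and a few lines of code; CAD and LAM results are already recorded for the fidelity measure. The complier-average interval is slightly wider than intention-to-treat, by roughly 1/0.94 = 1.06 at 94% receipt and 1/0.90 = 1.11 at 90%. Simulated widths agree: 0.133 and 0.139 against 0.125. When nearly everyone receives some component, the estimate will be close to intention-to-treat. Relabelling alone costs one sentence.

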## *Subgroup analyses*

For the primary outcome (TB treatment initiation) and for time-to-death outcome, we will analyse the intervention effect (RR) on outcomes by subgroups of those with and without TB in the differential diagnosis at admission (“TB suspects”) and by CD4 count. CD4 count measurement isn't a study specific activity, but where it is measured by hospital we will capture data, and we will analyses outcomes in subgroups CD4 = $<100$  cells/mm^3, CD4  $> 100$  cells/mm^3 and CD4 not measured. Where a person has more than one CD4 count measured in hospital, the CD4 count closest to admission will be used. P values for interaction will be reported.

## Missing data

No imputation will be performed for missing data. There will be no missing data for day recruited or cluster (i.e. arm) allocation. If an outcome is missing then it will be reported as such and not imputed.

No adjustment by baseline variables is planned, therefore missing data other than randomisation arm and outcome does not affect analysis. There is no imputation for missing covariates at baseline.

For the mortality secondary outcome (time to event), participants will be censored at the time they were last known to be alive.

## Additional analyses

The diagnostic cohort (which does not contribute to trial outcomes) will be analysed mainly using descriptive statistics.

Within trial arms, as an exploratory analysis, we will compare risk of death by 56 days from enrolment among those with HIV virological failure and those without HIV virologic failure. This will be in a subset of participants who have HIV viral load measured (a convenience sample based on when protocol amendment to collect HIV viral load and time of day of admission so that lab staff are available to process samples).

### **Harms**

Adverse events are defined in study protocol.

### **Statistical software**

The analysis will be carried out using R statistical software, and robust standard error calculated using 'sandwich' package and 'lmtest' package to adjust confidence intervals of glm. Packages 'survival' and 'survminer' will be used for survival analysis (secondary outcome).

Stata may also be used if necessary.

